7.5.5 Vital Signs, Physical Findings, and Other Observations Related to Safety

7.5.5.1 Vital Signs

Vital signs will include pulse (supine and standing), systolic/diastolic blood pressure (supine and standing), respiratory rate, body temperature, height, weight, and BMI will be listed by treatment group, subject, and visit date. Vital sign parameter measurements will be summarized by treatment group. Descriptive statistics will be presented for results and change from baseline at each visit where parameters were scheduled to be collected.

The number and percentage of subjects with a PCS measurement in supine will be presented by treatment group and study visit. PCS measurements include systolic blood pressure $\leq 90 \text{ mmHg}$, systolic blood pressure $\geq 180 \text{ mmHg}$, diastolic blood pressure $\leq 50 \text{ mmHg}$, diastolic blood pressure $\geq 105 \text{ mmHg}$, heart rate $\leq 40 \text{ bpm}$, and heart rate $\geq 120 \text{ bpm}$. PCS measurements in supine will also be listed.

Additionally, the number and percentage of subjects with an orthostatic systolic BP decrease > 20 mmHg or diastolic BP decrease > 10 mmHg from supine to standing position at any post-baseline measurement during the study will be summarized and listed.

7.5.5.2 12-Lead Electrocardiogram

Twelve-Lead ECG interval parameters including heart rate, PR, RR, QRS, QT, QTc interval calculated using the Fridericia method (QTcF), and QTc interval calculated using the Bazett method (QTcB) will be summarized by treatment group. Descriptive statistics will be presented for observed values and changes from baseline at each visit where parameters were scheduled to be collected.

The number and percentage of subjects with a PCS QTcF result will be presented by treatment group and study visit. PCS results at post-baseline visits include $QTcF \ge 500$ msec, QTcF change from baseline ≥ 60 msec, QTcF change from baseline ≥ 30 msec. PCS results at post-baseline visits will also be listed.

7.5.5.3 *Ophthalmology Examination*

Standard ophthalmologic examination and corneal specular microscopy examination results will be summarized by presenting shift from baseline to end of study results as normal, abnormal not clinically significant, and abnormal clinically significant. Clinically significant abnormalities on ophthalmologic exam will be listed by treatment group, subject, and visit date.

The baseline, post-baseline and percent (%) change from baseline of cell density and coefficient of variation (CV) results from the central reading group for CSM will be summarized descriptively for each eye (oculus dextrus [OD] and oculus sinister [OS]). The number and percentage of subjects with percent decrease from baseline in cell density \geq 5%, 10%, and 15% will be summarized for each eye and for both eyes. Results from the central reading group for CSM will also be presented in a data listing.

BlackThorn Therapeutics, Inc.	Statistical Analysis Plan
K2-MDD-201	Version 2.0; 03 June 2022

Additional subgroup summaries will be performed by three device types (Konan, Nidek and Tomey) and by age groups (18-29, 30-39, 40-49, 50-59, 60-65). All the above summaries will be repeated based on the set of subjects excluding the subjects who had endothelial dystrophy medical history prior to treatment.

7.5.5.4 *Physical Examination*

Abnormal results of the physical examination will be presented in subject data listings by treatment group, subject, and visit date.

7.5.5.5 Prior and Concomitant Medications

Medications will be coded using WHODrug (B3 Global) September 2019 version. Medications entered on the eCRF will be mapped to ATC drug class (level 4) and drug name. If ATC drug class level 4 is not available, then ATC drug class level 3 will be utilized. If ATC drug class levels 4 and 3 are not available, then ATC drug class level 2 will be utilized. If ATC drug class levels 4, 3, and 2 are not available, then ATC drug class level 1 will be utilized.

Prior and concomitant medications will be summarized separately and the study phase of each medication will be determined programmatically based on medication start and end dates. A prior medication is defined as any medication administered and stopped prior to the date of the first dose of study drug. A concomitant medication is defined as any medication administered on or after the date of the first dose of study drug. If it cannot be determined whether a medication was received after the start of study drug dosing, it will be considered concomitant.

For both prior and concomitant medications summaries, the number and percentage of subjects receiving any medication will be summarized by treatment group, as will the number and percentage receiving any medication by ATC drug class and generic drug name. Prior medications will also be summarized over all subjects combined. Subjects reporting use of more than one medication at each level of summarization (any medication received, ATC class, and generic drug name) will be counted only once. ATC class terms will be displayed by descending order of incidence, as will generic drug names within each ATC class. Prior and concomitant medications will be listed separately.

7.5.5.6 Prior and Concomitant Non-Pharmacological Procedures

Non-pharmacological procedures will be listed by treatment group, subject, and date.

7.5.5.7 Columbia Suicide Severity Rating Scale

Suicidality data collected on the C-SSRS at screening, baseline, and by visit during the treatment period will be listed for all subjects. Listings will include all data collected on the C-SSRS.

At screening visit, the number and percentage of subjects with a response of 'Yes' to:

- Any Suicidal Ideation from questions #1-3 (#1: Wish to be dead, #2: Nonspecific active suicidal thoughts, #3: Active suicidal ideation with any methods (not plan) without intent to act) for the past 3 months and each individual question #1-3 will be presented by treatment group
- The Preparatory Acts or Behavior question for the past 12 months will be presented by treatment group
- Any suicide attempts (Actual Attempt, Interrupted Attempt, or Aborted Attempt) in past 12 months will be presented by treatment group

At each of the scheduled visits following screening visit, the number and percentage of subjects with a response of 'Yes' to

- Any Suicidal Ideation from questions #1-5 (#1: Wish to be dead, #2: Nonspecific active suicidal thoughts, #3: Active suicidal ideation with any methods (not plan) without intent to act, #4: Active suicidal ideation with some intent to act, without specific plan, #5: Active suicidal ideation with specific plan and intent) or any Suicidal Behavior from questions for Actual Attempt, Interrupted Attempt, Aborted Attempt, or Preparatory Acts or Behavior will be presented by treatment group.
- Any Suicidal Ideation from questions #1-5 (#1: Wish to be dead, #2: Nonspecific active suicidal thoughts, #3: Active suicidal ideation with any methods (not plan) without intent to act, #4: Active suicidal ideation with some intent to act, without specific plan, #5: Active suicidal ideation with specific plan and intent) and each individual question #1-5 will be presented by treatment group.
- Any Suicidal Behavior from questions for Actual Attempt, Interrupted Attempt, Aborted Attempt, or Preparatory Acts or Behavior and each individual question will be presented by treatment group.

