3.2.2 Secondary

- Clinical Global Impression of Improvement (CGI-I) score assessed at each postbaseline timepoint
- Change from baseline to each timepoint assessed in SHAPS scores

BTRX-335140	BlackThorn Therapeutics, Inc.
Clinical Study Protocol Amendment 7	Date: 24Jan2022

- Change from baseline to each timepoint assessed in Hospital Anxiety and Depression Scale (HADS) subscales (ie, anxiety subscale [HADS-A] and depression subscale [HADS-D] scores)
- Change from baseline to each timepoint assessed in Hamilton Anxiety Rating Scale (HAM-A) total score
- Change from baseline to each timepoint assessed in Sheehan Disability Scale (SDS) scores
- Change from baseline to end of study in Clinical Global Impression Scale Severity (CGI-S) scores
- HAMD-17 response rate
- Assessment of safety through the occurrence of TEAEs, SAEs, and adverse events of special interest (AESIs); change from baseline in vital signs measurements, body weights, body mass index (BMI), clinical laboratory test results, C-SSRS scores, Clinical Opiate Withdrawal Scale (COWS) scores; physical examination findings, ECG results, and ophthalmologic examination findings.

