9.3.4.5 Clinical Laboratory Tests

Changes from baseline will be summarized for each laboratory test by study treatment and visit.

9.3.4.6 Electrocardiography

Electrocardiographic parameters will be listed. Clinically significant abnormalities on ECGs will be listed by subject and visit.

9.3.4.7 Ophthalmology

Ophthalmologic endpoints will be summarized. Clinically significant abnormalities on ophthalmologic exam will be listed by subject and visit.

9.3.4.8 Columbia Suicide Severity Rating Scale

Suicidality will be listed for all subjects.

9.3.4.9 Clinical Opiate Withdrawal Scale

COWS scale items and total scores, along with the numbers of subjects with a score of ≥ 5 , will be summarized at each visit by treatment group.

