7.5.5.8 Clinical Opiate Withdrawal Scale

The COWS will provide an ongoing assessment of subjects for any symptoms suggestive of opiate withdrawal. COWS scale items and total scores, along with the numbers of subjects with a total score of \geq 5, will be summarized by treatment group. Descriptive statistics for total scores and the number and percentage of subjects with a total score of \geq 5 will be presented for each visit that the COWS was scheduled to be administered.

Confidential

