7.7 Changes in the Conduct of the Study or Planned Analyses

There are no changes to the planned analyses described in the study protocol in this SAP.

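### The SAP plans no any-time post-dose count and no within-subject shift for the C-SSRS, so new or worsened suicidality by arm is not tabulated and would have to be counted from listings

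*SAP*

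**What the plan says.** Protocol 3.2.2 includes among the secondary safety measures "change from baseline in vital signs measurements, body weights, body mass index (BMI), clinical laboratory test results, C-SSRS scores"; the synopsis repeats this. The protocol's analysis section for the scale, 9.3.4.8, is narrower: "Suicidality will be listed for all subjects".

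SAP 7.5.5.7 goes further than 9.3.4.8. It plans:

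- a by-subject listing ("Listings will include all data collected on the C-SSRS");
- a screening table by arm, covering "Any Suicidal Ideation from questions #1-3" over the past 3 months, and preparatory acts and attempts over the past 12 months;
- after screening, "At each of the scheduled visits following screening visit, the number and percentage of subjects with a response of" Yes, for ideation or behavior combined, for ideation with each of items 1 to 5, and for behavior with each question.

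The SAP addendum does not mention the C-SSRS. SAP 7.1.2 maps scheduled and unscheduled assessments to windows and uses the scheduled record when a window holds one. SAP 7.1.5 takes the last pre-dose measurement as baseline.

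**The concern.** In a trial in major depressive disorder, a central safety question is how many subjects in each arm developed ideation or behavior on treatment that they did not have before, or got worse. By-visit rows do not answer it. The same subject can appear at several visits, so the rows cannot be added, and a Yes at a given visit may be persistent or new. A subject discontinued for suicidality also leaves the later rows, because percentages are by default based on subjects with available data (SAP 7.1.1).

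The protocol names change from baseline in this scale, and no planned table delivers it within subjects. If the count is first defined after unblinding, the choice of reference period is open to question, and that choice decides who counts as new.

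**Working it through.** The plan gives no figure to reproduce. The check is a comparison of passages, followed by bounds that show how much the by-visit rows leave open.

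**1. What the SAP does for other safety data**

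| Data | Subject-level summary planned |
|---|---|
| Laboratory tests (SAP 7.5.4) | Shift from baseline category to worst post-baseline value |
| Orthostatic blood pressure (SAP 7.5.5.1) | Subjects meeting the criterion at any post-baseline measurement |
| Adverse events (SAP 7.5.1) | Each subject counted once, at highest severity where severity is shown |
| Eye examinations (SAP 7.5.5.3) | Shift from baseline |
| C-SSRS (SAP 7.5.5.7) | None; by-visit counts and listings |

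**2. Unscheduled assessments**

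The C-SSRS is given at every scheduled and unscheduled visit (Protocol 6.3.7, SAP 6.4.2.9). SAP Table 4 has five post-dose C-SSRS windows: Weeks 2, 4, 6, 8 and 10. If a window holds a scheduled visit, that record is tabulated, and a positive unscheduled record in the same window appears only in the listing. The tables can therefore understate suicidality.

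**3. Bounds on subjects ever positive**

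Let x be the number positive at each of k post-dose assessments in an arm of N. From the rows alone,

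- minimum ever positive = x (the same subjects each time);
- maximum ever positive = the smaller of N and k·x (different subjects each time).

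Inputs: k = 5 (schedule of procedures, SAP Table 4). N = 180/2 = 90, an assumption from about 180 randomized 1:1. The values of x are assumed for illustration.

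| x per visit | Minimum | Maximum |
|---|---|---|
| 2 | 2 (2.2%) | 5·2 = 10 (11.1%) |
| 4 | 4 (4/90 = 4.4%) | 5·4 = 20 (20/90 = 22.2%) |
| 5 | 5 (5.6%) | 5·5 = 25 (27.8%) |
| 9 | 9 (10.0%) | 5·9 = 45 (50.0%) |

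The rows leave the any-time count undetermined by a factor of up to 5.

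**4. New onset**

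Visit 2 is a scheduled visit after screening, so it is tabulated too. Take x = 4 at Visit 2 as well. The rows then fit 0 new cases relative to Visit 2 (the same four persist) and 20 (all different). If nobody is positive at Visit 2, the range is 4 to 20. Group percentages before dosing narrow the range in that case but do not show who changed.

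**5. Where the ambiguity lies**

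Exclusion 3 (Protocol 4.1.2) removes subjects with a Yes on ideation item 4 or 5 in the 3 months before screening, or an attempt in the past 12 months. Protocol 4.4 requires discontinuation for ideation with intent or plan, or for any attempt. A post-dose Yes in those categories is thus largely new or worsened, and has few visits at which to recur. The uncertainty above applies mainly to items 1 to 3.

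**6. Reference period**

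Under SAP 7.1.5 the baseline is the Visit 2 form. That is the since-last-visit version, which reaches back only to screening. The screening form looks back 3 months and 1 year (Protocol 6.3.7). A subject with ideation only in the screening look-back is new against Visit 2 and not new against all pre-dose information. The documents do not say which applies.

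**The case against.** Most of the case against is an argument about strength, and several parts of it stand.

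- A reader might infer that the trial cannot report new or worsened suicidality. The documents do not support that: every response is collected and listed by subject and treatment group, so the counts can be derived. What is missing is a pre-specified table and definition.
- Screening and Visit 2 percentages are tabulated by arm, so a group-level comparison with pre-treatment status is available. Only the within-subject comparison is absent.
- A reader might infer that SAP 7.7 ("There are no changes to the planned analyses described in the study protocol in this SAP") is contradicted. For this scale it is not: the protocol's planned analysis is a listing, and the SAP exceeds it. The inconsistency is between Protocol 3.2.2 and 9.3.4.8.
- A reader might extend the point to the COWS, because SAP 7.5.5.8 stops at "Descriptive statistics for total scores and the number and percentage of subjects with a total score of" 5 or more by visit. But Protocol 9.1 already calls for change from baseline for continuous endpoints at each time point, which covers the COWS total. That is a minor alignment.
- The adverse event tables count each subject once and would pick up suicidality reported as an event. This cover is partial: Protocol 6.3.1 names laboratory, vital sign, ECG, eye and physical findings to be recorded as adverse events, but not C-SSRS responses.

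None of this supplies the any-time count or the shift.

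**Conclusion.** The point holds as a gap in pre-specified tabulation, with a cheap improvement available. A safety measure named in the protocol has no matching within-subject summary. In addition, the windowing rule can keep positive unscheduled assessments out of the tables.

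The size cannot be stated for this trial, because it depends on how often the same subjects recur. The illustrative range of 4 to 20 subjects rests on an assumed 90 per arm, with all 90 assessed at every visit, and on equal counts of 4 at each of five assessments. It overstates the uncertainty for items 4 and 5 and for attempts, given the entry and discontinuation rules. No data are lost, and the efficacy analyses are unaffected.

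**What to change.** Add to SAP 7.5.5.7 one Safety-population table by arm with:

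1. the number and percentage of subjects with any ideation, any behavior, or either after first dose, from all scheduled and unscheduled assessments including the follow-up call;
2. a shift from the worst pre-dose to the worst post-dose category.

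Define new and worsened before unblinding. State whether the pre-dose reference is Visit 2 alone or also includes the screening 3-month look-back. Showing both is preferable: a 3-month look-back is longer than the roughly two-week intervals after dosing and could mask new cases, while Visit 2 alone could label recurrent ideation as new.

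Bring Protocol 3.2.2 and 9.3.4.8 into agreement. As a minor alignment, state change from baseline for the COWS total in SAP 7.5.5.8.

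The cost is one table and a stated reference period, using data already collected. If the SAP can no longer be amended before unblinding, report the table in the clinical study report as an addition to the plan; SAP section 4 provides for documenting deviations there.

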7.5.5.8 Clinical Opiate Withdrawal Scale

The COWS will provide an ongoing assessment of subjects for any symptoms suggestive of opiate withdrawal. COWS scale items and total scores, along with the numbers of subjects with a total score of \geq 5, will be summarized by treatment group. Descriptive statistics for total scores and the number and percentage of subjects with a total score of \geq 5 will be presented for each visit that the COWS was scheduled to be administered.

Confidential

7.7 Changes in the Conduct of the Study or Planned Analyses

There are no changes to the planned analyses described in the study protocol in this SAP.

APPENDIX A: SCHEDULE OF PROCEDURES AND ASSESSMENTS

Period	Screening	Baseline		Study Drug	g Treatmen	ıt	Safety Fo	llow-up
Visit	1 ^b	2	3	4	5	6		
	Days -7 to -28	Day l	Day 15 (±2 d)	Day 29 (±2 d)	Day 43 (±2 d)	Day 57/ EOT ^c (±2 d)	TCª	Ocular Exam
Procedure and Assessments	NA	Week 0	Week 2	Week 4	Week 6	Week 8	Week 10	Week 12
Informed consent	Х							
Inclusion/exclusion criteria	Х	Xď						
Medical/psychiatric history	Х							
Demographics	х							
Vital signs ^e	Х	Х	x	х	х	х		
Physical examination ^f	Х							
Body weight ^g	Х	Х		х		х		
12-Lead ECG	Х	Х		х		х		
Standard ophthalmologic examination ^h		X ^{i, j}				x		
Corneal specular microscopy ^h		Xi						Xt
Prior/concomitant medication/therapy	x	x	x	x	x	x	x	
Randomization		Х						
Clinical laboratory tests (hematology, chemistry, urinalysis)	x	x	x	x	x	x		
Serum/urine pregnancy testk	Х	Х	x	х	х	х		
UDS (onsite and central laboratory) and breathalyzer alcohol screen	x	x	x	x	x	x		
Thyroid function tests	х							
Viral serology	Х							
Hepatic safety testing ⁿ	<							\longrightarrow
SCID-5-CT	Х							
CGI-S	Х	Х				х		
CGI-I		Х	x	х	х	х		
C-SSRS ^o	Х	х	Х	Х	Х	х	Х	
HAMD-17	Х	X		Х		х		
HAM-A	X	X		Х		x		
SDS		x		Х	Х	x		
HADS		х	x	Х	x	x		

Period	Screening	Baseline	Study Drug Treatment			Safety Follow-up		
Visit	1 ^b	2	3	4	5	6		
	Days –7 to –28	Day 1	Day 15 (±2 d)	Day 29 (±2 d)	Day 43 (±2 d)	Day 57/ EOT ^c (±2 d)	TC ^a	Ocular Exam
Procedure and Assessments	NA	Week 0	Week 2	Week 4	Week 6	Week 8	Week 10	Week 12
SHAPS	Х	Х		Х		Х		
COWS	Х	Х	Х	Х	Х	Х		
Adverse events ^p		Х	Х	Х	Х	Х	Х	
Complete IWRS	Х	Х	Х	Х	Х	Х		
Dispense study drug		Xq	Xq	Xq	Xq			
Study drug administration		Xr		Xs				
Study drug compliance			Х	Х	Х	Х		

BMI = body mass index; CRF=case report form; CGI-I = Clinical Global Impression of Improvement; CGI-S = Clinical Global Impression of Severity; COWS = Clinical Opiate Withdrawal Scale; CSSRS = Columbia Suicide Severity Rating Scale; d = day; DSM = Diagnostic and Statistical Manual of Mental Disorders; ECG = electrocardiogram; eCRF=electronic case report form; EOT = End of Treatment; HADS = Hospital Anxiety and Depression Scale; HAM-A = Hamilton Anxiety Rating Scale; HAMD-17 = Hamilton Rating Scale for Depression – 17Item Version; IWRS = Interactive Web-response System; NA = not applicable; SDS = Sheehan Disability

- ^a Study site personnel will contact subjects by telephone for Safety Follow-up assessments (adverse events, concomitant medication usage, and C-SSRS) approximately 2 weeks after discontinuation of study drug.
- ^b Visit 1 procedures may be completed over 2 days, if necessary.
- ^c Subjects who discontinue early will complete an EOT visit <2 days after their last dose of study drug; efficacy assessments are to be performed only if the subject has remained on study drug. For subjects who do not return, the site should complete a C-SSRS if they are aware of a potential suicide-related thought or behavior by other communications. The 12-week corneal specular microscopy examination should still be conducted approximately 12 weeks after the first dose of study drug (Section 7.7.2 of the protocol).

- ^d Inclusion/exclusion criteria must be reconfirmed for eligibility prior to randomization.
- ^e Collect vital signs measurements (respiratory rate first, then blood pressure and pulse) after subject has been supine for 10 minutes; subjects should then stand for 3 minutes before obtaining standing vital signs measurements [see Section 6.3.4 of the protocol]. Oral temperature can be assessed in any position.
- ^f A full physical examination involving an evaluation of cardiovascular, respiratory, gastrointestinal, neurological (examination of cranial nerves, motor system, sensory, and reflexes), dermatological, and musculoskeletal systems, and include general appearance, skin, head, neck, eyes, ears, nose, throat, lungs, heart, abdomen, back, lymph nodes, extremities, and vascular status will be conducted at the screening visit. Further physical examination will be conducted as needed. (Section 6.3.3 of the protocol).
- ^g At Screening, collect height for BMI calculation.
- ^h Ophthalmologic examinations will be performed by a site-affiliated ophthalmologist. Details for the standard ophthalmologic examination and corneal specular microscopy will be described in a separate ocular monitoring manual. Additional standard ophthalmologic exams and / or corneal specular microscopies may be conducted to assess subject safety.
- ⁱ Baseline ophthalmologic examinations (standard and corneal specular microscopy) must be performed before randomization.
- ^j Prior to Visit 3 (Week 2) (between Days 7 and 14 [+2 days]), a standard ophthalmologic examination will be performed.

k Serum pregnancy test is to be performed at screening visit only and urine pregnancy tests will be performed by the site at all subsequent visits.

1				
m				

- Unscheduled hepatic monitoring testing may be performed at any time on the basis of clinical laboratory testing results, after consultation with the Sponsor-designated medical monitor (see Section 6.3.2.2 of the protocol).
- 0 The C-SSRS Baseline version will be used at Screening and "Since Last Visit" version will be used for all subsequent visits.
- р Adverse events reported before first dose of study drug to be recorded as medical history. Serious AEs will be recorded on the AE eCRF from the time of informed consent.
- q Subjects will be instructed to take their study drug daily in the morning and preferably with food.
- Subjects will take their first dose of study drug (BTRX-335140 or placebo) under the supervision of clinical study personnel during the baseline visit. s
- t The Week 12 corneal specular microscopy should be completed for all subjects (ie, completers and early termination) unless consent is withdrawn. The corneal specular microscopy should be conducted approximately 12 weeks after the first dose of study drug; exceptions to be discussed with the medical monitor.

